## **17.0 Data Management\* and Confidentiality**

### Data Management:

All study parameters from the EMR will be downloaded by an EMR specialist via a report, de-identified, and housed in a Microsoft Excel database. Patient forms, including consent forms, will be stored in a locked file cabinet at Maple Tree Cancer Alliance. All patients will be assigned a Study ID number and a list linking patient names to Study ID number will be kept separately from the study data, on a password-protected computer. Data from patient forms will be entered into the master Microsoft Excel spreadsheet. Only Study ID will be used to identify patients in the spreadsheet.

### Data Analysis Plan:

Data will be analyzed using IBM SPSS Statistics version 25.0. Continuous variables will be described using mean, median, standard deviation, and range. Nominal variables will be described using frequency and percentage.

Baseline demographic and clinical characteristics will be compared between treatment and control groups to establish equivalence; any statistically significant differences between study groups will be controlled statistically. Continuous endpoints will be tested for normality using Shapiro-Wilk tests. Differences between study groups on continuous endpoints will be evaluated using independent samples *t*-tests for normally distributed endpoints and Mann-Whitney *U* tests for non-normally distributed endpoints. Nominal endpoints will be compared between groups using chi-square tests. Alpha will be set to .05, two-tailed for all tests.

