## 2.0 Objectives\*

The primary objective is to test the effect of an individualized exercise oncology program on healthcare utilization, 30-day hospital readmission, pain, and cancer treatment tolerance.

H1: Among women newly diagnosed with stage 0, 1 or 2 breast cancer, those enrolled in an individualized exercise oncology program will have fewer emergency room (ER) visits, fewer hospital encounters, fewer 30-day hospital readmissions, fewer breaks in cancer treatment, less pain, and better cancer treatment tolerance than those in the control group over 3 months.

The secondary objective is to examine the feasibility of an individualized exercise oncology program via adherence and attrition rates.

H2: Among women newly diagnosed with stage 0, 1 or 2 breast cancer and enrolled in an individualized exercise oncology program, adherence to scheduled exercise sessions will average 70% or more, and program attrition will average 70% or less over 3 months.

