## **4.0 Study Endpoints\***

### Primary Study Endpoints:

- Total number of missed fractions, determined via EMR
- A break in cancer treatment, defined as missing  $\geq 3$  fractions due to patient condition, determined via EMR
- ER visits, as determined via EMR
- Inpatient and outpatient hospital encounters, as determined via EMR
- Hospital readmission for the same presenting issue, as determined via EMR
- Hospital length of stay (if hospitalized), as determined via EMR
- Cancer treatment adherence, determined via EMR
- Medications for cancer treatment symptom management, determined via EMR
- Cancer treatment-related side effects, determined via EMR
- Patient-rated pain measured by visual analog scale, as determined via EMR
- Cancer treatment tolerance, measured by the Eastern Cooperative Oncology Group (ECOG) Performance Status score, as determined via EMR
- Quality of Life, as measured by the McGill Quality of Life Measure, administered in-person at weeks 1 and 12  
[\(http://www.npcrc.org/files/news/mcgill\\_quality\\_of\\_life.pdf\)](http://www.npcrc.org/files/news/mcgill_quality_of_life.pdf)

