### Demographic and Baseline Clinical Characteristics:

- Age, as determined via electronic medical record (EMR)
- Diagnosis and diagnostic stage, as determined via EMR
- Diagnosis Date, as determined via EMR
- Body mass index, as determined by height and weight in EMR
- Comorbid chronic conditions (hypertension, diabetes, COPD), as determined via EMR
- Race/ethnicity, as determined via EMR

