## 6.0 Procedures Involved\*

The study design is an open-label, randomized, controlled, parallel-group trial. Women age 30-80 with a recent diagnosis of stage 0, 1 or 2 breast cancer who meet inclusion and exclusion criteria will be invited to participate. As is typical and customary, a diagnosis within the last 12 weeks will be considered a recent diagnosis. Upon study enrollment and informed consent, patients will be randomly assigned to the Exercise Group or the Control Group. Random assignment will be conducted in blocks of 10 to ensure equal groups (See Appendix A). Participants will be enrolled in the study for 12 weeks.

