## 15.0 Risks to Subjects\*

The risks associated with the study intervention are commensurate with light to moderate physical activity, such as muscle soreness. Given the low-impact nature of the exercise and the one-on-one supervision during exercise sessions, the risk of injury or another adverse outcome is very low. Participants in the Exercise Group will have an exercise program individualized to their needs and physical abilities, and participants will be closely monitored during exercise sessions. The

**PROTOCOL TITLE:** Randomized, Controlled Trial of an Individualized Exercise Oncology Program for Newly Diagnosed Breast Cancer Patients

study will not be blinded; patients and treating physicians will be aware of group status and if the treating oncologist recommends the subject stop physical activity, the subject will be withdrawn from the study.

The Exercise Group may incur some travel costs to attend exercise sessions.

No psychological, social, or legal risks are anticipated.

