## **22.0 Consent Process**

All patients will be fully informed about the study and will have time to ask questions and consider their decision to participate. A research intern for Maple Tree Cancer Alliance, [name], will provide a written informed consent form to eligible patients and meet with them in person to discuss the study in a private room at the Kettering Cancer Center or the Soin Cancer Center. Patients will be provided with the informed consent form and the intern will go through the information in the form with the patient. Patients will be invited to take the form home and talk with family and friends before deciding if they would like to participate. If patients wish to take some time to make the decision, they may inform the intern about their decision to participate or decline participation via phone.

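### Covariates are chosen by baseline significance tests with no adjusted model named, and the week-1 McGill score has no stated use in the analysis

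*Combined protocol and SAP*

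**What the plan says.** The Data Analysis Plan in section 17.0 compares baseline demographic and clinical characteristics between groups, with the aim of showing the groups equivalent. It then states that "any statistically significant differences between study groups will be controlled statistically". The between-group tests it names are the independent-samples t-test or Mann-Whitney U for continuous endpoints and chi-square for nominal ones. The choice between the first two follows a pre-test: "Continuous endpoints will be tested for normality using Shapiro-Wilk tests". No regression, ANCOVA or stratified method is named.

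Section 4.0 lists six items under "Demographic and Baseline Clinical Characteristics": age, diagnosis and stage, diagnosis date, body mass index, comorbidities, and race/ethnicity. McGill is not among them. It appears as the last of the 12 primary endpoints: "Quality of Life, as measured by the McGill Quality of Life Measure, administered in-person at weeks 1 and 12". It is not named in the primary objective or in H1 (section 2.0), which ends with "fewer breaks in cancer treatment, less pain, and better cancer treatment tolerance than those in the control group over 3 months".

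On timing, section 6.0 says "Upon study enrollment and informed consent, patients will be randomly assigned to the Exercise Group or the Control Group". Section 15.0 adds that the "study will not be blinded; patients and treating physicians will be aware of group status". Nothing places the week-1 form before or after assignment.

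**The concern.** There are two linked gaps.

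**The rule.** In a randomised trial, baseline differences arise by chance. A significance test therefore picks covariates by accident, not by how strongly they predict the outcome. A non-significant result in a small trial is not evidence of equivalence. When the rule fires, the plan does not say what is fitted, so the analyst settles the model with the data in hand.

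**McGill.** The trial collects the measure twice, but does not say whether the endpoint is the week-12 score or the change, or what the first score is for. The candidate analyses differ in power by amounts that matter at 35 per group. Leaving the choice open either gives up precision the trial has already paid for or leaves a primary analysis to be chosen afterwards.

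**Working it through.** **Inputs from the documents.** 35 per group (section 12.0); two-sided alpha .05 (section 17.0); six baseline items, or nine if diagnosis and stage are separated and the three comorbidities are counted singly (section 4.0).

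**Assumptions.** The documents give neither a McGill effect size nor a week-1 to week-12 correlation. I take d = 0.5 SD and show r from 0.1 to 0.7. The only power figure in the plan, 80% in section 12.0, concerns missed fractions and is not an input here.

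**Step 1: what non-significance can show.** The smallest significant baseline difference is t(.975, 68 df) × sqrt(2/35) = 1.9955 × 0.2390 = 0.48 SD. Imbalances of up to nearly half an SD would pass as equivalent.

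**Step 2: how often chance triggers the rule.** For independent variables, 1 − 0.95^6 = 0.265 and 1 − 0.95^9 = 0.370. Correlated variables would change these figures.

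**Step 3: what the rule costs for the listed baseline covariates.** Simulation, 100,000 trials per setting, adjusting only when the baseline test gives p < .05:

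| Covariate-outcome r | Power, triggered rule | Power, pre-specified adjustment | Type I error, triggered rule |
|---|---|---|---|
| 0.1 | 54.1% | 54.0% | 5.0% |
| 0.2 | 53.8% | 55.0% | 4.8% |
| 0.3 | 53.9% | 57.2% | 4.8% |

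The loss is at most about 3 points, with no inflation of type I error.

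**Step 4: McGill, first form completed before assignment.** Formulas (noncentral t, noncentrality = effect × sqrt(35/2)):
- Unadjusted week-12 score: effect 0.5, df 68. Power 54.1%.
- ANCOVA: effect 0.5/sqrt(1 − r²), df 67. At r = 0.5 this is 0.577, power 66.3%.
- Change score: effect 0.5/sqrt(2(1 − r)), df 68. At r = 0.5 this is 0.5, power 54.1%.

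The ANCOVA formula ignores chance imbalance in the first score. The simulated column includes it and is the one to use.

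| r | Unadjusted | Change score | ANCOVA, formula | ANCOVA, simulated | Gain over unadjusted |
|---|---|---|---|---|---|
| 0.1 | 54% | 34% | 54% | 54% | nil |
| 0.3 | 54% | 41% | 58% | 57% | 3 points |
| 0.5 | 54% | 54% | 66% | 66% | 12 points |
| 0.6 | 54% | 64% | 73% | 73% | 18 points |
| 0.7 | 54% | 76% | 82% | 82% | 28 points |

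ANCOVA beats the change score at every r shown, by 20 points at r = 0.1 and 6 at r = 0.7. At r = 0.5 with d = 0.4 or 0.6, the unadjusted test gives 38% or 70% and ANCOVA 47% or 81%. Applying the triggered rule to the first McGill score would recover almost nothing: 54 / 55 / 55% (40,000 simulated trials) at r = 0.3 / 0.5 / 0.7, apart from small simulation error.

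**Step 5: skewed scores.** For an assumed moderate left skew (reflected gamma, shape 4), Shapiro-Wilk applied per group, 5,000 trials per setting, d = 0.5:

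| r of underlying normals | Plan's t/Mann-Whitney switch | Plain ANCOVA | Rank-based ANCOVA |
|---|---|---|---|
| 0.3 | 60% | 57% | 63% |
| 0.5 | 61% | 65% | 70% |
| 0.7 | 60% | 81% | 85% |

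**The case against.** The strongest reply is that the rule does little measurable harm. That stands: step 3 shows a small power loss and no inflation of type I error. A reader might infer that the rule produces false positives; the calculation does not support that. The fault is discretion over an unnamed model.

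A reader might also infer that the week-1 score is discarded. The documents do not say so: no week-12 comparison is defined, and a t-test on change scores, which would use the first score, is not excluded. Nor is it certain that the rule misses McGill, because section 17.0 does not tie its baseline characteristics to the section 4.0 list. The supported statements are that the score has no stated use and that the rule does not clearly reach it.

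The gain is conditional, and that also stands. If the first form follows assignment in this open-label trial, knowing the group could shift the score. ANCOVA would then move the estimate by minus r times the shift; an assumed 0.2 SD shift toward Exercise at r = 0.5 turns 0.50 into 0.50 − 0.5 × 0.2 = 0.40. This is a hazard of the proposed ANCOVA, not harm done by the present plan, and it is why the order must be fixed first.

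Finally, McGill is one of 12 primary endpoints, and not the one used for the sample size. The gain does not extend to missed fractions or to other endpoints without a baseline value. It is tempting to include pain, but no section shows that a pre-randomisation value exists in the medical record. On skew, step 5 favours the rank-based analysis on power, and plain ANCOVA falls about 3 points below the plan's switch at r = 0.3.

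**Conclusion.** The point holds in a limited form. The adjustment rule is data-driven, has no named model and cannot establish equivalence. Its chance of firing is about 26-37% if the variables are independent, but its cost is small: about 3 points of power at most for assumed r up to 0.3. The material loss is confined to McGill, where neither the endpoint nor the use of the first score is stated. With d = 0.5 and a pre-assignment form, both assumed, pre-specified ANCOVA gains nothing over the unadjusted test at r = 0.1, 3 points at r = 0.3, 12 at r = 0.5 and 28 at r = 0.7. It is better than the change score throughout. This is worth correcting, but it does not call the trial's validity into question.

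**What to change.** - Delete the significance-triggered rule and report baseline characteristics descriptively, without tests.
- Require the first McGill form after consent and before the assignment is revealed.
- Define the McGill endpoint as the week-12 score and pre-specify ANCOVA on group and first score, with no Shapiro-Wilk switch for this endpoint.
- Keep plain ANCOVA primary, because it estimates a mean difference on the McGill scale. Pre-specify rank-based ANCOVA as a sensitivity analysis, because it may have more power if scores are skewed.

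The cost is plan wording plus one regression and one rank-based analysis in the software already named. No extra patients or forms are needed. There are two downsides. McGill is given in person, while section 22.0 says of patients who take time to decide that "they may inform the intern about their decision to participate or decline participation via phone", so for them assignment may have to wait until the form is completed. And plain ANCOVA may lose a few points of power under skew at low correlation.

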## **9.0 Study Timelines\***

Patient recruitment will begin after IRB approval is obtained. Each patient will be enrolled in the study for 12 weeks. Study enrollment is expected to take place over approximately 6 months, until 70 patients are enrolled. When 70 patients have been enrolled, enrollment will close, and active subjects will be followed for the remainder of their 12 week participation. Once all patients have completed the study, data will be abstracted from the EMR and analyzed within 12 months.

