## 12.0 Local Number of Subjects

A total of 70 subjects will be enrolled (35 in each study group). This sample size provides 80% power to detect a medium effect size in number of missed treatment fractions between study groups. Only subjects who meet eligibility criteria will be enrolled.

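### Twelve primary endpoints are each tested at two-sided .05, and no rule says which result, or how many, would confirm H1

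*Combined protocol and SAP*

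**What the plan says.** Under the heading "Primary Study Endpoints", section 4.0 gives twelve bullets: missed fractions, treatment breaks, ER visits, hospital encounters, readmission, length of stay, treatment adherence, symptom medications, side effects, pain, ECOG status and quality of life. None is marked as the deciding one.

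H1 in section 2.0 predicts "fewer emergency room (ER) visits, fewer hospital encounters, fewer 30-day hospital readmissions, fewer breaks in cancer treatment, less pain, and better cancer treatment tolerance" over 3 months. That is six outcomes joined by 'and', with no statement of how many must be significant.

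Section 12.0 bases the 70 patients (35 per group) on "80% power to detect a medium effect size in number of missed treatment fractions". Missed fractions is therefore the only endpoint used for sample size, and it is also listed first in section 4.0. It is not designated as the deciding endpoint, and H1 does not name it.

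The Data Analysis Plan in section 17.0 assigns a *t*-test, Mann-Whitney test or chi-square test according to the type of endpoint, and then says "Alpha will be set to .05, two-tailed for all tests". No section gives an adjustment, an order of testing or a composite.

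**The concern.** A plan with several primary endpoints has to say how they combine into one conclusion. Three readings of this plan are possible: any one significant result supports H1, all six H1 outcomes must be significant, or each outcome is a separate claim. They have very different error rates and power, and the text does not choose between them.

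The endpoint list and H1 also do not map onto each other cleanly.

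- The endpoint used for sample size is missing from H1, which names breaks instead.
- H1 refers to 30-day readmissions, while the endpoint is "Hospital readmission for the same presenting issue, as determined via EMR", with no window.
- "Inpatient and outpatient hospital encounters, as determined via EMR" could be one test or two.

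The trial is open-label and is meant to inform cost savings and the place of exercise in routine care (section 3.0). Without a rule, one favourable result among many could be reported as confirming the primary objective, at an error rate above the one stated.

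**Working it through.** **Inputs from the documents.** Twelve primary endpoints (section 4.0); six H1 outcomes (section 2.0); two-sided alpha .05 per test (section 17.0); 35 per group and 80% power for a medium effect on missed fractions (section 12.0). Correlations, event rates and a numerical effect size are not given, so those used below are assumptions.

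**Step 1: the plan's own figure.** Take medium as d = 0.5 (assumption). The two-sample *t*-test at 35 per group has noncentrality 0.5 × √(35/2) = 2.09 on 68 degrees of freedom, which gives 54% power. The stated 80% is reached only at d = 0.68. This matters here because it is the power left for a single continuous primary endpoint.

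**Step 2: any one result counts.** Under the global null, for *k* independent tests:

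- six H1 outcomes, results favouring exercise only: 1 − 0.975^6 = 14.1%
- six H1 outcomes, either direction: 1 − 0.95^6 = 26.5%
- all twelve, either direction: 1 − 0.95^12 = 46.0%
- thirteen, if inpatient and outpatient encounters are tested separately: 1 − 0.95^13 = 48.7%

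For correlated tests, assume normal test statistics with a common correlation ρ. The chance is 1 − ∫ φ(x) [P(one test not significant | shared factor x)]^k dx, evaluated numerically:

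| Set | Nominal | ρ = 0 | 0.5 | 0.7 | 0.9 |
|---|---|---|---|---|---|
| Six H1 outcomes, favouring exercise | 2.5% | 14% | 10% | 8% | 5% |
| All twelve, either direction | 5% | 46% | 32% | 23% | 13% |

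**Step 3: why independence is an upper illustration.** Section 4.0 derives one endpoint from another: "A break in cancer treatment, defined as missing" three or more fractions is a threshold on missed fractions. Readmission and length of stay arise only among patients with a hospital encounter. Rare events also make single tests conservative. The exact size of the uncorrected chi-square test at 35 per group is 0.5% when the event rate is 2% and 3.6% at 5%. It is 5.7% at 10%, so the reduction applies only to very rare events. As an illustration, if four of twelve independent tests had size 0.5%, the 46% would become 1 − 0.95^8 × 0.995^4 = 35%.

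**Step 4: all six must be significant.** No inflation is possible. A false claim requires at least one true null to be rejected in the favourable direction, so the rate is at most 2.5% for tests that hold their level. Under the global null it is 0.7% at ρ = 0.9, 1.1% at 0.95 and 1.8% at 0.99. Power is the difficulty. If all six outcomes were continuous with d = 0.5, simulation gives 3%, 17%, 25% and 38% at ρ = 0, 0.5, 0.7 and 0.9. Breaks are binary, so these figures are only a guide. If breaks fell from an assumed 10% to 5%, chi-square power in the favourable direction would be about 12%, which caps the power of the whole rule.

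**Step 5: adjustment across several primaries.** At d = 0.5 and 35 per group, Bonferroni power per endpoint is 27% at .05/6 and 20% at .05/12.

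**The case against.** The strongest reply is that the plan already implies a rule.

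- *H1 joins its outcomes with 'and'.* Read literally, all six must succeed, and nothing is inflated. But H1 states what is expected, not what must be significant. On that reading, quality of life and the other primary endpoints outside H1 would decide nothing.
- *Missed fractions is first in the list and drives the sample size.* A reader might infer that it is the primary endpoint in practice. The documents do not support this: no section designates it, and H1 omits it. Section 10.0 does not require radiotherapy, so some patients may have no fractions to miss.

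A second reply is that 46% is the least favourable framing, since it needs twelve bullets, errors in either direction and independence. This stands. H1 is directional and names six outcomes, so the 14% to 5% range is the closer match to a claim for exercise. Overlap and very rare events pull the figures down further.

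A third reply concerns readmission. A reader might infer that sections 2.0 and 4.0 contradict each other. They can be read together as readmission within 30 days for the same issue. The wording is incomplete, not clearly in conflict.

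**Conclusion.** The concern holds as a missing decision rule. Twelve endpoints share primary status, each is tested at .05, and nothing states what confirms H1.

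The size depends on the reading. If any one of the six H1 outcomes counts in favour of exercise, the error rate is about two to nearly six times the nominal 2.5% over assumed correlations from 0.9 down to 0. If any of the twelve counts in either direction, it is roughly 2.7 to 9 times the nominal 5%. These figures assume equally correlated normal statistics and tests of correct size. If all six H1 outcomes must be significant, there is no inflation and power is low.

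A reader might infer that the trial has a 46% type I error rate. The documents do not support that. The plan never says that any one result suffices, and its endpoints are not independent. What can be said is that the plan does not exclude such a reading, so the error rate of its primary conclusion is undefined.

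**What to change.** Settle the rule before the data are seen. Section 9.0 leaves room for this: "Once all patients have completed the study, data will be abstracted from the EMR and analyzed within 12 months".

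1. Name one primary endpoint that is covered by the objective and H1 and measurable in all randomised patients. The choice is the sponsor's. If it is missed fractions, add it to H1 and state how the analysis handles patients without radiotherapy.
2. Put in section 17.0: *H1 will be judged on [endpoint] alone, tested at two-sided .05. All other endpoints now listed as primary in section 4.0 become secondary and are reported as between-group differences with 95% confidence intervals, without a confirmatory claim.* The feasibility endpoints (adherence, attrition) and the safety endpoints keep their current status.
3. If several primaries are kept, apply Holm across them or state that all must be significant.
4. Use one readmission definition in sections 2.0 and 4.0: the 30-day window, the same presenting issue, or both.
5. Restate section 12.0 for the chosen endpoint. For a continuous endpoint, the Step 1 figures apply.

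The cost is wording in sections 1.0, 2.0, 4.0, 12.0 and 17.0, with no extra patients. The downside is that eleven endpoints lose primary status and the stated power becomes less favourable. Keeping six or twelve primaries avoids the first loss, but at the lower power per endpoint shown in Step 5.
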